#### Data Analysis/Statistics

This pilot study is largely descriptive to determine the feasibility and preliminary effectiveness of MERA. Due to the small sample size, all alpha levels will be set at 0.1 with the goal of maximizing the chance of detecting statistical differences.

Aim 1: Veteran verbal feedback, collected at the end of the third MERA session, will be examined to improve the acceptability of the training. Frequencies will be calculated on the number of Veterans who were referred, completed the screen, completed the pretraining assessment, met eligibility criteria, and attended all 3 emotion regulation training sessions.

Aim 2. Our second aim was to explore changes in aggression and emotion dysregulation from pre- to post-treatment among patients who completed MERA. Given study attrition and our desire to use as much data as possible, the statistical design for the primary analyses was an intent-to-treat, mixed effects regression model examining the main effect of time as the effect of substantive interest. Analyses were conducted using the generalized linear mixed models module in SPSS Version 24 using data from all sessions. Data transformations using appropriate link functions given the nature of the data (e.g., log transformation due to significant skewness in the OAS across all time points), where necessary, were conducted. Results were back translated into the original metric for ease of interpretation. Where appropriate, pairwise comparisons between time points were examined to determine which time points differed from one another. Effect sizes are reported to provide context for statistically significant results. Finally, percentages were provided for the frequency of veterans' engagement in an EBP after MERA (Exploratory Aim).

Exploratory Aim. Frequencies will be used to examine the number of PTSD evidence-based psychotherapy sessions to determine initiation, engagement, and completion rates following MERA.

ADVERTISEMENT: Bulletin Board

Exact language of Advertisement:

Male Veterans Who Served in Afghanistan or Iraq

Manage Emotions to Reduce Aggression

Do you have PTSD and struggle to manage aggression? We are researching a 3-session emotion-regulation training that is designed to help Veterans manage emotions and decrease aggression.

Study Involves:

- 3 treatment training sessions
- 2 assessment sessions

If interested in learning how to decrease your aggression and also want to help other Veterans by evaluating the treatment, please call

[name] at [contact] [name], Principal Investigator

Offered by James A. Haley

Veterans Affairs Hospital.

Funded by the Department

of Veteran Affairs'

Consortium to Alleviate PTSD.

IRB# 23884

Payment:

Veterans will not be paid for taking part in the 3-session training. However, they will be compensated for the pre and post-training assessments. After completing the pre-training assessment, each Veteran will receive a \$30.00 by direct deposit to his bank account. If he is eligible for the study based on screening questions and complete the training, he will complete a post-treatment assessment and receive a \$30.00 by direct deposit after the assessment. If you do not have a bank account, you can be paid by check. That is a maximum of \$60.00 if both assessments are completed.

Veterans will receive a Form 1099 from the VA, which is required to process their payments. This form requires that study staff to use whole social security number instead of just the last 4 digits.

Costs: There are no costs associated with the study over and above the costs that would be incurred from standard care or services. For VA patients, there may be co-payment costs for some of the non-research procedures for which the VA may not pay even if these occur while you are participating in this research. Some veterans are required to pay co-payments for medical care and services provided by the VA. These co-payment requirements will continue to apply to medical care and services provided by the VA that are not part of this study and that you would receive as part of your regular medical care.

**5. Sample size:** We request to consent up to 60 participants to account for potential dropouts. We aim for a sample of 30 Veterans. The final goal is to have complete pre- and post-treatment data for 20 participants. Up to 25 participants may need to complete the post-treatment assessment in order not to slow recruitment at the end of the study.

**6. Study Population with Inclusion/Exclusion Criteria:** Veterans enrolled at the Tampa VA and who meet the following criteria will be recruited to the study:

Inclusion criteria: 1.) Male Veteran who served in OEF/OIF/OND. 2.) Currently meets criteria for a PTSD diagnosis, determined by the Clinician-Administered PTSD Scale-5. 3.) Engaged in at least 3 self-reported impulsive aggression acts (e.g., yelling, throwing objects, hitting objects/people) in the last month, measured by the Overt Aggression Scale. 4.) Impulsive aggression is his/her primary form of aggression, determined by having a higher Impulsive Aggression subscore than a Premeditated Aggression subscore on the Impulsive Premeditated Aggression Scale. 5.) Because aggressors are poor historians when reporting their aggression frequency, each Veteran must agree to allow an independent aggression rater (a person with whom the Veteran has a long-standing, close personal relationship and has in-person interaction most of the days of the week; ) verify the number of aggressive acts, using the Overt Aggression Scale. 6.) No psychotropic medication change for six weeks prior to the assessment and agreement not to ask for a medication change for the duration of the study.

Exclusion criteria: Veterans who meet the following criteria will be excluded: 1.) Previously began PE or CPT. 2.) Is currently suicidal with intent of self-harm in the last week. 3.) Is currently homicidal with plans to hurt a specific person. 4.) Is unable to complete self-report measures. 5.) Does not have an independent aggression rater. 6.) Has severe alcohol consumption patterns (Alcohol Use Disorders Identification Test), severe drug use consumption patterns (Drug Use Disorders Identification Test), active psychosis, or mania (MINI). 7.) Had a psychotropic medication change within 6 weeks prior to the pretraining assessment. Veterans receiving general mental health services or non- PE or CPT psychotherapy will be allowed to participate in this study.

**7. Expected Results (Publication and Presentation Plans):** The PI plans to publish a manuscript describing the results of the pilot project after the final data are collected in 2019. Data will be presented in aggregate form, or if case studies are written, all information will be disguised with no identifying information.

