- b) The Emotion Regulation Questionnaire (ERQ) is a 10-item self-report measure with 2 factors that assess specific emotion regulation strategies: cognitive reappraisal (changing the way one thinks about a situation) and expressive suppression (not expressing the emotion outwardly but feeling it internally). More effective emotion regulation is indicated by higher cognitive reappraisal scores and lower expressive suppression scores. Internal-consistency estimates (alpha) were .80 for the reappraisal factor and .73 for the suppression factor in a college-student sample, and both were greater than .75 in a Veteran sample. Scoring is based on how well the items describe the individual in the past week, from 1 (strongly disagree) to 7 (strongly agree).
- 7) Aggression.
  - a) The Impulsive Premeditated Aggression Scale (IPAS) is a 30-item self-report measure that assesses impulsive and premeditated aggression. In psychiatric outpatients, Cronbach's alphas were .82 and .77 for premeditated aggression and impulsive aggression, respectively. Scoring is based on how well each item describes an individual's aggressive acts, from 1 (strongly disagree) to 5 (strongly agree). To determine eligibility for the study, the measure will be scored in a categorical method by calculating the total percentage of positive items ("strongly agree" or "agree") for each aggression subscale and classifying the Veteran as either a primarily impulsive or premeditated aggressor, based on which subscale has the highest percentage of positive items. The summed dimensional score for the impulsive aggression subscale will be used to examine pre to posttraining differences in impulsive aggression.
  - b) The Overt Aggression Scale (OAS) is a 17-item self-report measure that assesses frequency of different aggression acts, including verbal and physical aggression against self, other, and objects. Intraclass correlation coefficients of reliability ranged from .89-.99 in 2 adult psychiatric samples. The measure will be adapted for the current study to indicate frequency of each aggressive act over the past week. Aggressive acts will be summed to create a total score.

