The CAPS-5 will be administered by a master's level independent evaluator. The assessment session will be audio taped; to estimate interrater agreement, a random 3% of tapes will be evaluated by the study staff. After the pre-training assessment, study staff will review the Veteran's answers to the self-report questionnaires and the structured interviews. If the Veteran meets inclusion criteria and does not meet exclusions criteria, then study staff will call the Veteran within 7 days to notify him that the study appears to be an appropriate fit and alert him of when the next treatment session will be. If the Veteran does not meet criteria, study staff will call the Veteran (within 7 days) and explain that the study does not appear to be a good fit for the Veteran. All Veterans will already be established within the VA and will be reminded of their next mental health appointments. If the Veteran desires additional resources, the PI will complete appropriate requests via the electronic medical records.

If Veterans are found to be eligible they will obtain a baseline level of aggression (and reduce retrospective bias), by completing an aggression tracking forms (OAS) during the approximate 2 weeks between the pretraining assessment and the treatment sessions. Because Veterans may inaccurately report aggressive acts, an inclusion criterion is an independent aggression rater who is willing to verify aggressive acts. This is clearly stated in the informed consent and will be explained to the Veteran. Study staff will contact the independent aggression rater by phone and read the OAS to him/her (See Independent Aggression Rater Script). This should take less than 10 minutes. Aggression frequency reported by the independent aggression rater and Veteran will be compared to determine whether the Veteran's report is accurate. This information will be helpful in determining recruitment procedures for the subsequent studies/grant.

Veterans who do not meet the inclusion criteria or meet exclusion criteria will be referred back to the appropriate clinic, either General Mental Health Clinic or PTSD Clinical Team, depending on the Veteran's needs. If a Veteran needs immediate treatment (e.g., suicidal intent, active psychotic symptoms), s/he will be referred for immediate evaluation following standard VA emergency protocols. Veterans will be able to engage in usual care during the study.

Assessment schedule
----------------------------

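### The Aim 2 analysis does not say whether or how the independent rater's pre-to-post OAS is used, although the protocol requires a rater because it distrusts self-reported aggression

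*Combined protocol and SAP*

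**What the plan says.** **Analysis.** The Aim 2 paragraph of Data Analysis/Statistics covers change in aggression and emotion dysregulation. It uses an "intent-to-treat, mixed effects regression model examining the main effect of time as the effect of substantive interest", fitted "using data from all sessions". It mentions the OAS once, as an example of skewness, without saying who completed it. The rater does not appear anywhere in that section.

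**Why there is a rater.** Section 6 makes a rater a condition of entry (inclusion criterion 5, exclusion criterion 5) and gives the reason: "Because aggressors are poor historians when reporting their aggression frequency". Item 7(c) of the measures adds that impulsive aggressors may remember their acts poorly and may confuse anger with aggression.

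**What the rater supplies.** Item 7(c), the Assessment schedule and the Posttraining assessment paragraph all have the rater complete the OAS before and after MERA, by telephone.

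**What is done with it.** The one described analysis is under the pretraining assessment procedures: "Aggression frequency reported by the independent aggression rater and Veteran will be compared to determine whether the Veteran's report is accurate". Its purpose follows: "This information will be helpful in determining recruitment procedures for the subsequent studies/grant". No statistic is named.

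**The aggression outcomes.** The OAS "is a 17-item self-report measure that assesses frequency of different aggression acts" and is listed under primary outcomes in the schedule. The IPAS impulsive subscale, also self-report, is given an explicit pre-to-post use in item 7(a).

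**The concern.** The trial is open, has one arm and has no masking. The estimated effect is a before-after change in what Veterans report about themselves. If reporting drifts between the two assessments, the drift goes straight into the estimate, and there is no control arm to subtract it.

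The drift could go either way. Item 7(c) warns that a Veteran who still feels anger may not notice improvement, which would hide a real fall. Under-reporting after an unmasked training would exaggerate a fall or create one.

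The second informant, seen at both times, is the one source that could help to separate the two. A comparison at one time point shows how accurate the Veteran's report is then. It does not show whether accuracy changed, and only a change in accuracy biases a before-after result. With no analysis specified, the rater's change could also be reported or left out after the results are seen.

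**Working it through.** **1. Text check.** There is no figure in the plan to reproduce: it gives no SD, effect size or power. The check is therefore whether any section specifies an analysis of the rater's change.

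| Place | What it gives for the rater's OAS |
|---|---|
| Measures, item 7(c) | Collected before and after; purpose is verification |
| Pretraining assessment procedures | Compared with the Veteran's report; no statistic; aimed at later recruitment |
| Assessment schedule | Marked at pre and post |
| Posttraining assessment | Repeat call, in the paragraph on detecting change for Aim 2 |
| Data Analysis/Statistics | Not mentioned |
| Section 6 | Reason for requiring a rater; no analysis |

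The Posttraining paragraph suggests that some Aim 2 use may be intended. No section says what it is.

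**2. How a reporting shift would appear (illustration).** Inputs from the plan: alpha 0.1 (Data Analysis/Statistics) and a goal of 20 complete pairs, with up to 25 possible (section 5). Assumptions: a two-sided test, because the plan does not state sidedness; a paired contrast in place of the mixed model; approximately normal changes; and SD meaning the SD of within-person pre-to-post change.

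With no real change and a shift of δ SD, the chance of a significant fall is P(T > t(0.95, 19)), where T is noncentral t with 19 df and noncentrality δ√20, and t(0.95, 19) = 1.729.

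| δ (assumed) | Noncentrality | Chance of a significant fall |
|---|---|---|
| 0 | 0 | 5% |
| 0.2 | 0.89 | 22% |
| 0.3 | 1.34 | 36% |
| 0.4 | 1.79 | 53% |
| 0.5 | 2.24 | 70% |

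**3. Precision of the rater's own change.** 90% half-width = t(0.95, n−1)/√n, in SD units.

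- n = 25: 1.711/5 = 0.34
- n = 20: 1.729/4.472 = 0.39
- n = 15 (assumption: a quarter of 20 post calls missed): 1.761/3.873 = 0.45

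**4. Precision of the Veteran-minus-rater difference in change.** If both reporters have the same SD of change and their changes correlate ρ (both assumptions), multiply the half-width by √(2(1−ρ)). At n = 20:

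- ρ = 0.3: 0.387 × 1.183 = 0.46
- ρ = 0.5: 0.387 × 1.000 = 0.39
- ρ = 0.7: 0.387 × 0.775 = 0.30

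A 0.5 SD shift confined to the Veteran's reports would be detected at the same alpha in 57%, 70% and 87% of trials respectively.

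**5. How often a real fall would earn rater support.** If the rule is that the rater's whole 90% interval must show a fall, the calculation is the same as in step 2. At 20 pairs, a true rater-observed fall of 0.3, 0.5 or 0.8 SD meets it in 36%, 70% or 96% of trials.

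**The case against.** **Use may be intended.** The statistics section lists few measures and does not say whose OAS it means. The repeat rater call is in the paragraph on Aim 2 change, and verification of aggressive acts is a stated purpose at both time points. This stands in part. One cannot say that the aggression result will rest on self-report alone, only that the plan does not say whether or how the rater's change enters it.

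**Three stronger readings are tempting, and the documents do not support them.**

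- A reader might infer that "using data from all sessions" excludes the rater, who has two occasions against the Veteran's five. But the DERS and the IPAS also have only two occasions, and the DERS is listed as a primary outcome.
- A reader might infer exclusion because the CAPS-5 and IPAS entries state a pre-to-post use and the rater entry does not. But the DERS and Veteran OAS entries state none either, and both are listed as primary outcomes.
- A reader might infer that rater and Veteran report over different periods, because inclusion criterion 3 counts acts "in the last month, measured by the Overt Aggression Scale" while the measures section has the OAS "adapted for the current study to indicate frequency of each aggressive act over the past week". But criterion 3 concerns the Veteran's eligibility. No section gives the rater a different window, and the natural reading is the past week for both. A sentence confirming this is enough.

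**The numbers are assumed.** That is correct. They show how the design responds to a shift, not that one will occur.

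**It is a small descriptive pilot with unmasked raters, so a descriptive sentence would do.** The limits are real: a bias shared by both reporters would go undetected, and at 20 pairs the wording rule withholds support from a true 0.3 SD fall in 64% of trials (100 − 36). But Aim 2 tests at alpha 0.1 and is meant to give preliminary evidence of effectiveness. A descriptive sentence with no rule set in advance leaves open what a disagreement would mean.

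**Conclusion.** The concern holds as a gap in specification that affects what the trial may conclude. The protocol requires a second informant because it regards self-report as unreliable and collects that informant's OAS at both ends, but it specifies no analysis of the change. The described outcome measures of aggression are self-report in an uncontrolled trial, so as written a change in reporting could pass for a change in aggression.

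The size of any bias cannot be stated from the documents. The 22% to 70% range is illustrative; it rests on assumed shifts of 0.2 to 0.5 SD and a paired approximation to the mixed model. The precision figure, about ±0.39 SD at 20 pairs, does not depend on an assumed shift, but it uses the same approximation and assumes that all 20 Veterans have both rater calls.

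The point is worth acting on because the data are already scheduled. The gain is modest.

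**What to change.** In the Aim 2 paragraph of Data Analysis/Statistics:

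1. Name the rater's pre-to-post OAS change as a supporting Aim 2 outcome. Keep the Veteran's OAS as primary.
2. Analyse it with the same type of model and the same link or transformation, at pre and post only.
3. Report side by side, with 90% intervals, the Veteran's change, the rater's change and the Veteran-minus-rater difference in change, together with the number of rater calls completed at each time.
4. State that the rater answers over the same past-week window as the Veteran, at both calls.
5. Fix the wording in advance. A fall is described as supported by the rater only if the rater's whole 90% interval shows a fall. Otherwise it is described as self-report only, and the report says whether the rater data contradict it (for example, the interval for the difference in change excludes zero, with the larger fall in the Veteran's reports) or are merely too imprecise.
6. Part of the Aim 2 paragraph is in the past tense. If that analysis has already been run, label this one as added afterwards.

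**Cost.** A few sentences and one small model; both rater calls are already scheduled. The aggression conclusion may become less favourable. The check is partial: raters are unmasked, do not see every act, and at 20 pairs give an interval of about ±0.39 SD, so a self-report-only result will often reflect imprecision rather than disagreement.

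### The OAS analysis blurs a log link with a log transformation and names no distribution, so the treatment of zero weekly counts and the meaning of the back-translated values are undefined

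*Combined protocol and SAP*

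**What the plan says.** Section 4 (Design/Procedure), in the aggression measures, adapts the OAS to record the "frequency of each aggressive act over the past week. Aggressive acts will be summed to create a total score". The score is therefore a non-negative count. The assessment schedule lists it under primary outcomes at five points: pretraining, each of the three sessions, and posttraining.

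The Aim 2 paragraph of Data Analysis/Statistics plans an "intent-to-treat, mixed effects regression model examining the main effect of time as the effect of substantive interest". On software and data it says: "Analyses were conducted using the generalized linear mixed models module in SPSS Version 24 using data from all sessions". It then refers to "Data transformations using appropriate link functions given the nature of the data", with the OAS as the example: "log transformation due to significant skewness in the OAS across all time points". On reporting it says: "Results were back translated into the original metric for ease of interpretation".

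The paragraph names no distribution, gives no rule for zero counts, mentions no added constant, and does not say what quantity the back-translated value estimates.

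**The concern.** The paragraph can be read in two ways, and they give different analyses.

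- **Log link.** The model is for log(E[Y]). A zero count is an ordinary observation if the distribution allows it, and exponentiated contrasts are ratios of mean counts.
- **Log transformation.** The model is for E[log Y]. log(0) does not exist, so zero records are lost or a constant c must be added. Exponentiated results are geometric-type means.

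The wording mentions link functions, but it calls the step a transformation and justifies it by skewness. Skewness is a reason to log the response. A link acts on the mean and does not address skewness; the choice of distribution does, and none is named. Even with a log link, a positive-only distribution such as the gamma cannot use zeros.

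Zero weeks are the best outcome the training can produce. If they are lost, the estimated change moves toward no effect. A reader also could not tell whether a reported number of acts per week is an arithmetic or a geometric mean. Finally, resting the choice on skewness seen across all time points makes it depend on the outcome data.

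**Working it through.** The documents state no OAS mean, dispersion, zero rate or power figure, so there is no figure to reproduce. The check asks whether zeros are likely and what each reading does to them.

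**Step 1: are zeros plausible?** Section 6 requires that the Veteran has "Engaged in at least 3 self-reported impulsive aggression acts" in the last month. With 30.4/7 = 4.34 weeks per month, the minimum is 3/4.34 = 0.69 acts per week. The chance of a zero week at mean m is exp(−m) for a Poisson count and (k/(k+m))^k for a negative binomial count with size k.

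| Acts per month | Mean per week | P(0), Poisson | P(0), neg. bin. k = 1 |
|---|---|---|---|
| 3 | 0.69 | 0.50 | 0.59 |
| 12 | 2.76 | 0.06 | 0.27 |
| 24 | 5.53 | 0.004 | 0.15 |

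These are chances before any improvement.

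**Step 2: an assumed effect.** Assume a mean of 6 pretraining and 2 posttraining, negative binomial, k = 1.5. The true ratio is 2/6 = 0.33.

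- P(0) pretraining = (1.5/7.5)^1.5 = 0.09
- P(0) posttraining = (1.5/3.5)^1.5 = 0.28

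With p(y) the negative binomial probability, the back-translated value is exp{Σ p(y) log(y + c)} − c. With zeros dropped, it is exp of the mean of log y over y > 0.

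| Handling | Pre | Post | Post/pre |
|---|---|---|---|
| Log link on the mean | 6 | 2 | 0.33 |
| log y, zeros dropped | 4.73 | 2.20 | 0.46 |
| log(y + 1) | 4.16 | 1.39 | 0.33 |
| log(y + 0.5) | 3.88 | 1.22 | 0.31 |
| log(y + 0.1) | 3.34 | 0.86 | 0.26 |

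Dropping zeros turns a 67% fall into a 54% fall. Over k = 0.7 to 3 its ratio is 0.43 to 0.51.

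A log link with a positive-only distribution sees means of m/(1 − P(0)). These are 6/(1 − 0.09) = 6.6 and 2/(1 − 0.28) = 2.8, a ratio of 0.42.

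**Step 3: other assumptions.** Take a true ratio of 0.50 and k = 1, with 400,000 simulated counts per time point.

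| Pretraining mean | Log link | Zeros dropped | log(y + 1), back-translated | log(y + 0.1), back-translated |
|---|---|---|---|---|
| 0.69 | 0.50 | 0.85 | 0.234/0.461 = 0.51 | 0.094/0.208 = 0.45 |
| 3 | 0.50 | 0.68 | 0.980/1.900 = 0.52 | 0.522/1.191 = 0.44 |
| 10 | 0.50 | 0.58 | 3.103/6.035 = 0.51 | 2.175/4.779 = 0.46 |

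**Step 4: does a log-link count model run on data with zeros?** Poisson and negative binomial log-link models were fitted by GEE, as a stand-in for the mixed model, to 20 simulated pre/post pairs. Both used all 40 records, 7 of them zero, and returned exactly the ratio of the raw means.

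**The case against.** The strongest reply is that the log appears only as a bracketed example in a sentence about link functions, within a generalized linear mixed model. Read as a log link with a count distribution, the plan already keeps every zero and needs no constant. That reading is available and stands. It is why the point concerns an undefined specification and not a demonstrated error.

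Three stronger inferences are tempting and are not supported:

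- **That Veterans who stop being aggressive are dropped, or that a constant is added.** The documents say neither. Even if zeros were lost, a mixed model using all sessions would lose the zero-count records. A Veteran would drop out entirely only if all his OAS records were zero.
- **That the added constant largely sets the effect.** In the Step 2 scenario, comparing values on the y + c scale gives 0.46, 0.39 and 0.28 for c = 1, 0.5 and 0.1. The plan reports in the original metric, so the constant should be subtracted; the spread then narrows to 0.33, 0.31 and 0.26. For c = 1 the ratio happens to match the truth, although the mean of 4.16 is still not 6.
- **That the main Aim 2 result is at risk.** The OAS is one of several outcomes. The Difficulties in Emotion Regulation Scale is also listed as primary, and Section 4 names the impulsive subscale of the Impulsive Premeditated Aggression Scale for change in impulsive aggression.

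It is also fair that the study is an uncontrolled, largely descriptive pilot, and that a negative binomial model is not the only remedy. A Poisson model with log link and robust standard errors would also keep zeros. Neither point supplies the missing distribution or says what the back-translated number is.

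**Conclusion.** The concern holds in a conditional form. The plan does not settle whether the log applies to the mean or to the response, names no distribution for a count that can be zero, and ties the choice to observed skewness.

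If the response is logged and zeros are dropped, or a positive-only distribution is used, the ratio moves toward 1: 0.46 or 0.42 against a true 0.33 in the assumed case. If a constant is added and removed consistently, the ratio is less affected (0.26 to 0.33), but the reported pretraining level is 3.3 to 4.2 acts per week where the mean is 6. Under a log link with a count distribution none of this arises.

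All sizes rest on assumed means and dispersion, and they come from marginal counts at two time points, not from the planned five-point mixed model. The direction of the drop-zeros distortion was the same in every case tried. The plan should be changed because the remedy is specific, fits the framework already chosen and costs little.

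**What to change.** In the Aim 2 paragraph of Data Analysis/Statistics, replace the log-transformation example with text such as:

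*OAS totals will be analysed with a negative binomial mixed model (log link, time as a categorical fixed effect, random Veteran intercept) using all records including zeros, with no added constant. This model will be used whatever the observed skewness. We will report the posttraining/pretraining rate ratio with its confidence interval and model-based mean acts per week at each time point.*

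State also whether those means are averaged over the random intercept or refer to a Veteran with intercept zero. With a normal intercept of variance σ² they differ by the factor exp(σ²/2), while the ratio is unaffected. Any log-transformed analysis should be a sensitivity check, with its constant and back-translation stated.

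The Aim 2 paragraph is written in the past tense. If the analysis has already been run, report the distribution and zero handling actually used and give this model beside it.

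The cost is a few sentences of text and one estimated dispersion parameter, which will be imprecise with about 20 completers. No new data are needed.
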